3.2. Study Duration, Enrollment and Number of Subjects

The duration of each subject's participation is expected to last approximately 1 month.

The entire study is expected to last approximately 3 years.

We will screen up to 100 people to identify 25 mild asthmatics who experience a LPR to inhaled cat hair allergen extract and are eligible for enrollment into the Anakinra therapy trials.

3.3. Study Population

Inclusion Criteria:

1. Age range 18-45 years, inclusive
2. FEV₁ of at least 80% of predicted and FEV₁/FVC ratio of at least 0.7 (without use of bronchodilator medications for 8 hours or long acting beta agonists for 24 hours), consistent with lung function of persons with no more than mild intermittent or mild persistent asthma.
3. Physician diagnosis of asthma
4. Allergic sensitization to cat hair extract as demonstrated by positive immediate skin prick test response or serum cat IgE >0.35 kU/L.
5. Negative pregnancy test for females who are not s/p hysterectomy with oophorectomy or who have been amenorrheic for 12 months or more.
6. Oxygen saturation of >94% and blood pressure within the following limits: Systolic between 150-90 mmHg and Diastolic between 90-60 mmHg.

Exclusion Criteria:

1. Clinical contraindications:
 - a. Any chronic medical condition considered by the PI as a contraindication to participation in the study including significant cardiovascular disease, diabetes, chronic renal disease, chronic thyroid disease, history of chronic infections or immunodeficiency.
 - b. Physician directed emergency treatment for an asthma exacerbation within the preceding 12 months.
 - c. Exacerbation of asthma more than 2x/week which could be characteristic of a person of moderate or severe persistent asthma as outlined in the current NHLBI guidelines for diagnosis and management of asthma.
 - d. Daily requirements for albuterol due to asthma symptoms (cough, wheeze, chest tightness) which would be characteristic of a person of moderate or severe persistent asthma as outlined in the current NHLBI guidelines for diagnosis and management of asthma (not to include prophylactic use of albuterol prior to exercise).
 - e. Viral upper respiratory tract infection within 4 weeks of challenge.
 - f. Any acute infection requiring antibiotics within 6 weeks of challenge or fever of unknown origin within 6 weeks of challenge.
 - g. Severe asthma

- h. Mental illness or history of drug or alcohol abuse that, in the opinion of the investigator, would interfere with the participant's ability to comply with study requirements.
 - i. Cigarette smoking >1 pack per month
 - j. Nighttime symptoms of cough or wheeze greater than 1x/week at baseline (not during a clearly recognized viral induced asthma exacerbation) which would be characteristic of a person of moderate or severe persistent asthma as outlined in the current NHLBI guidelines for diagnosis and management of asthma.
 - k. Allergy/sensitivity to study drugs or their formulations, including a history of anaphylaxis following exposure to cat allergen.
 - l. Known hypersensitivity to methacholine or to other parasympathomimetic agents
 - m. History of intubation for asthma
 - n. Unwillingness to limit coffee, tea, cola drinks, chocolate, or other foods containing caffeine after midnight on the days that methacholine challenge testing is to be performed.
 - o. Unwillingness in females to use reliable contraception if sexually active (IUD, birth control pills/patch, condoms).
2. Pregnancy or nursing a baby. Female volunteers will be asked to use effective birth control (stable regimen of hormonal contraceptive use for at least 3 months, intrauterine device placement, tubal ligation or endometrial ablation for at least 3 months through at least one week after study completion) and will provide a urine sample to test for pregnancy on study days. If the test is positive or the subject has reason to believe she may be pregnant, she will be dismissed from the study. Women who have been amenorrheic for 12 months may participate.
3. Usage of the following medications:
- a. Use of systemic steroid therapy within the preceding 12 months for an asthma exacerbation. All use of systemic steroids in the last year will be reviewed by a study physician.
 - b. Subjects who are prescribed daily inhaled corticosteroids, cromolyn, or leukotriene inhibitors (Montelukast or Zafirlukast) will be required to discontinue these medications at least 2 weeks prior to their screening visit.
 - c. Use of daily theophylline within the past month.
 - d. Use of allergen immunotherapy.
 - e. Use of any immunosuppressant therapy within the preceding 12 months will be reviewed by the study physician.
 - f. Receipt of LAIV (Live Attenuated Influenza Vaccine), also known as FluMist®, or any other live viral vaccine within the prior 30 days, or any vaccine for at least 5 days
 - g. Use of beta blocking medications
 - h. Antihistamines in the 5 days prior to allergen challenge
 - i. Routine use of NSAIDs, including aspirin.
4. Physical/laboratory indications:
- a. Abnormalities on lung auscultation
 - b. Temperature >37.8 C
 - c. Oxygen saturation of <94%
 - d. Systolic BP>150 mmHg or <90 mmHg or diastolic BP>90 mmHg or <60 mmHg
5. Inability or unwillingness of a participant to give written informed consent.

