Arvidsson et al¹⁷ also conducted a study of lower airway responses to inhalation of cat allergen extract (Aquagen® SQ, ALK-Abello). Aqueous dilutions of cat extract were aerosolized and inhaled in increasing concentrations using a dosimeter nebulizer with tidal breathing until a drop in FEV1 of 20% or greater was observed. The starting dose of 13.75 standard quality (SQ) allergen concentration was increased up to a maximum cumulative dose of 7026 SQ. In this study, all 62 participants achieved an EPR with a drop of at least 20% from baseline FEV1 during the first 2 hours, and 56% achieved a LPR with a drop of at least 15% from baseline during the 3 to 24 hours following the EPR. No clinically severe early or late phase reactions were reported during this study.

Lieutier-Colas et al¹⁸ conducted a study of the effects of particle size on early phase response to inhaled cat allergen (Stallergenes Laboratories, Antony, France). Participants inhaled increasing concentrations (0.5 to 100 Indice de Reactivite (IR)) of aerosolized cat allergen solution from different nebulizers producing particles of different sizes (1.4 to 10.3 μ m). A dosimeter was also used in this study to control for inspiratory flow and puff duration to ensure standardized dosing and deposition in the airways. They found that the provocative dose of cat allergen was significantly lower when inhaling larger particle size (10.3 μ m compared to 1.4 μ m) and more comparable to environmental cat exposure. LPR drops in FEV1 did not differ by particle size of inhaled cat allergen.

Brussino et al¹⁹ examined oxidative stress in exhaled breath condensates following inhaled cat allergen (Stallergenes Laboratories, Antony, France) challenge in asthmatic humans. The initial inhalation dose was determined based on a mathematical formula incorporating end point skin prick titration testing and methacholine PC₂₀. Of the 12 study participants, all experienced a 20% or greater drop in FEV1 (mean 26% \pm 2.6) during the EPR. During the LPR, the mean drop in FEV1 was 17% \pm 1.9.

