2.2. Secondary Objective

In addition to identifying subjects for participation in the planned studies of Anakinra vs placebo for mitigating features of asthma exacerbation, the additional purpose of this study is to determine if IL-1 β concentrations in the sputum at baseline before challenge are predictive of key asthma outcomes following inhaled allergen challenge, specifically:

- a). maximum drop in %FEV1 during LPR
- b). Change in methacholine reactivity from baseline pre-allergen measurement to 24 hours after allergen challenge.
- c). exhaled nitric oxide (eNO) level
- d). induced sputum:
 - i. Granulocyte (neutrophils/eosinophils) numbers and percentages
 - ii. Mucins (secretion of MUC5AC and MUC5B determined by Western blot and ELISA)

Additionally, as exploratory endpoints, we will assess the effects of allergen challenge on markers of systemic inflammation and changes in inflammatory gene expression as described below:

- a). **venipuncture** for assessment of systemic inflammatory markers (CBC with differential for absolute neutrophil count and absolute eosinophil count), pro-inflammatory cytokine levels such as IL-1 β , IL-6, IL-8).
- b). **gene array analysis** from blood and induced sputum at the baseline visit, again on the day of the challenge and, finally, at 24 hours post challenge. To identify signaling pathways potentially impacted by allergen challenge, we will use Nanostring® technology to measure differential expression of a panel of 594 immunology-related genes. This will be accomplished by collecting and isolating peripheral blood mononuclear cells from venous blood samples collected before allergen challenge, during allergen challenge, and 24 hours after allergen challenge.
- c). **heart rate variability** measurement via commercially-available monitor (Space Labs, Inc). We will identify if specific cardiac changes occur during allergen-induced asthma exacerbation.
- d). **environmental sensors** developed through the National Science Foundation-funded Center for Advanced Self-Powered Systems of Integrated Sensors and Technologies (ASSIST) program will be worn by participants during inhaled allergen challenge. These health and exposure tracker devices include an ECG chest patch and a wrist band that will measure Heart Rate, motion and ambient temperature and ozone concentration.

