4.2. Intervention/Treatment procedures

Visit 2: Methacholine Challenge Day (at least 2 days but less than 2 weeks after the baseline visit V1)

1. Review any change in medical status since last visit
2. Vital signs, oxygen saturation, and symptom score
3. Urine pregnancy test
4. Baseline HRV measurement
5. eNO
6. Spirometry
7. Physical exam of the ears, nose, throat and chest

8. Methacholine challenge if inclusion and exclusion criteria are still met (refer to section 5.4 for methacholine challenge procedure)

Visit 3: Allergen challenge day (24-48 hours after V2)

1. Review any change in medical status since last visit
2. Vital signs, oxygen saturation, and symptom score
3. Placement of the HRV device
4. Placement of the ASSIST devices (cardiac electrodes and wrist band)
5. eNO
6. Collect nasal ELF
7. Spirometry
8. If inclusion and exclusion criteria are still met, allergen challenge will be performed as described in section 5.1.
 - a. If subject is asymptomatic and FEV1 drops $<10\%$ at the completion of allergen challenge, subjects will be monitored for 2 hours post challenge and will be discharged following post-challenge venipuncture with rescue medications (albuterol with aerochamber and oral prednisone 60 mg), instructions for use of these medications if asthma symptoms occur, and contact information for the on-call physician. Subject will resume protocol beginning with Study visit 4 detailed below.
 - b. Any subject whose FEV1 drops $\geq 10\%$ will stay for the 10 hour post-allergen monitoring period as outlined below.
9. Collect nasal ELF after completion of the allergen challenge, either following the dose producing a 20% or greater fall in FEV1 (in early phase responders) or following completion of the highest dose of inhaled allergen (in those who do not exhibit an early phase response).
10. Post-challenge monitoring of vital signs every 10 minutes for the 1st hour, then every 30 minutes until 2 hours post-challenge, then hourly until 10 hours post-challenge
11. Spirometry when vital signs are obtained
12. eNO hourly between 2 and 10 hours post-challenge
13. Collect nasal ELF at 7 hours post-challenge (7 hours after the onset of the early phase response).
14. Venipuncture for CBC with diff, cytokines, and gene expression 10 hours post-challenge (approximately 50 cc total)

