15. All subjects will receive 4 puffs of albuterol 10 hours post-challenge. Spirometry will be performed 15 minutes after albuterol if post-challenge FEV1 at 10 hours was not approximately within 10% of baseline.
 - a. Albuterol will be repeated every 20 minutes up to three doses if repeat FEV1 is not within approximately 10% of baseline value or if subject remains in distress.
 - b. If needed, after three inhaled albuterol treatments, additional medications, including nebulized albuterol, atrovent and oral prednisone 60mg, will be given per physician discretion.
16. Subjects will be discharged 10 hours following allergen challenge when clinically stable and when FEV1 is within approximately 10% of baseline FEV1. HRV monitoring will be discontinued prior to discharge. At discharge, all subjects will be provided with an albuterol inhaler and aerochamber, a single dose of oral prednisone 60 mg, clear instructions for use of rescue medications in the event of symptoms related to bronchoconstriction, and contact information for the on-call physician. Subjects will reside overnight at their home if their residence is within 10 miles of UNC or a local hotel within 10 miles of UNC.

Visit 4: 24 hours post challenge

1. Vital signs, oxygen saturation, and symptom score
2. eNO
3. Spirometry
4. Venipuncture for CBC with Diff, gene expression, cytokines (approximately 50 cc total).
5. Methacholine challenge.
6. Sputum induction.
7. Collect nasal ELF.

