Following the measurement of FEV₁ after the first 7 minute inhalation period, the concentration of saline will be increased from 3% to 4%, provided the FEV₁ decrement is < 10% from the post-bronchodilator value. If the FEV₁ falls between 10-20% of the post bronchodilator value, the test will proceed but the concentration of saline will remain the same. If the FEV₁ falls by > 20% or if troublesome symptoms occur, the nebulization will be discontinued, and albuterol will be immediately available if necessary to relieve symptoms. The same procedure will be followed for the final 7 minute inhalation period using 5% hypertonic saline provided the FEV₁ safety parameters described above have been met. The nebulization is stopped after a total of 21 minutes or earlier if a sputum sample of good quality is obtained (i.e. visible sputum plugs).

5.3. Spirometry:

Standard methodology conforming to the American Thoracic Society/European Respiratory Society guidelines for measurement of spirometry will be used²²

5.4. Methacholine Challenge:

This test measures the responsiveness of the airways to a standard cholinergic bronchoconstriction agent. Methacholine challenge testing is a standard clinical procedure to determine airway reactivity in patients with known or suspected airway disease. Subjects will be asked to limit caffeine on the day of testing. Subjects will inhale 5 breaths from the nebulizer at each concentration starting with saline control. Each breath is started from resting end-expiratory lung volume (Forced Residual Capacity) and continued until a maximum inhalation is reached. Increasing (doubling) concentrations are inhaled until the FEV₁ falls by at least 20% from the post saline value, the highest concentration has been inhaled, or the subject experiences discomfort or anxiety sufficient for the investigator or subject to consider further testing unacceptable. Methacholine concentrations will be 0.075, 0.156, 0.312, 0.625, 1.25, 2.5, 5.0, and 10.0 mg/ml. If subjects experience symptoms that do not rapidly and spontaneously remit at the end of the procedure, he/she will receive 4 puffs of an inhaled bronchodilator (albuterol) MDI. If needed an additional 4 puffs or a nebulizer treatment with standard dose albuterol (0.083mg) will be given. The subject will not be discharged until spirometry levels return to baseline.

5.5. Venipuncture:

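### Caffeine is limited only on methacholine days, so the allergen challenge day, which carries the primary FEV1 endpoint and the challenge HRV recording, has no limit

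*Combined protocol and SAP*

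**What the plan says.** Caffeine appears in two places. In section 3.3, exclusion 1n concerns willingness to limit caffeinated drinks, chocolate and other "foods containing caffeine after midnight on the days that methacholine challenge testing is to be performed". Section 5.4, which describes the methacholine procedure, adds: "Subjects will be asked to limit caffeine on the day of testing".

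Section 4.2 fixes the days. The first methacholine test has its own visit: "Visit 2: Methacholine Challenge Day (at least 2 days but less than 2 weeks after the baseline visit V1"). The second is at Visit 4, 24 hours after the allergen challenge. The allergen challenge stands between them: "Visit 3: Allergen challenge day (24-48 hours after V2"). The procedures table in section 15.1 agrees: methacholine at Visits 2 and 4, allergen at Visit 3.

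The primary endpoint (sections 2.1, 6.1 and 6.3) is a fall in FEV1 of at least 15% during hours 3-10, so it is measured at Visit 3. Section 5.1 takes the FEV1 after the diluent inhalation on that day as baseline.

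For HRV, Visit 2 lists a "Baseline HRV measurement" (item 4). At Visit 3 the device is placed before the challenge and monitoring ends before discharge. The stated aim in section 2.2 is: "We will identify if specific cardiac changes occur during allergen-induced asthma exacerbation". Section 6.3 classes HRV as exploratory.

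**The concern.** The plan controls caffeine when an FEV1 fall is read after methacholine, but not when an FEV1 fall is read after allergen, although the second reading is the primary endpoint. Nothing in the text explains the difference.

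Several hard cut-offs apply on the uncontrolled day. A fall below 10% moves the subject up the allergen ladder. If the subject is still below 10% and asymptomatic at the end, he or she goes home after 2 hours and counts as a screen failure. A fall of 20% stops the challenge. A late fall of 15% defines a responder. If caffeine moves FEV1 at all during the stay, subjects close to one of these lines could be classified differently.

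For HRV, the measurement labelled baseline and the challenge recording are made under different caffeine instructions. A comparison of the two would mix that difference with whatever the challenge does.

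**Working it through.** The plan states no figure on this point, so the check is to map the caffeine rule onto the visit schedule and the pre-challenge requirements.

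**Step 1. Visits covered** (sections 3.3, 4.2, 5.4, 15.1)

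| Visit | Methacholine | Allergen | Primary FEV1 endpoint | HRV | Caffeine limit |
|---|---|---|---|---|---|
| 1 | no | no | no | no | no |
| 2 | yes | no | no | labelled baseline | yes |
| 3 | no | yes | yes | challenge recording | no |
| 4 | yes | no | no | no | yes |
| 5 | no | no | no | no | no |

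The Visit 4 limit starts at midnight of that day. With a daytime challenge (an assumption) it does not reach back into Visit 3 monitoring.

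**Step 2. Whether another rule closes the gap at Visit 3.** Section 5.1 requires 8 hours without bronchodilators. The morning-of-challenge criteria in section 9.4 repeat this and add anticholinergics and antihistamines. Neither mentions caffeine. Visit 3 item 8 asks that eligibility criteria still be met, but exclusion 1n is itself confined to methacholine days, so that check adds nothing. No listed Visit 3 procedure asks about caffeine.

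**Step 3. Whether the difference follows from how the two tests are read.** The methacholine fall is measured against the same-day value after saline (section 5.4). The allergen fall is measured against the same-day value after diluent (section 5.1). The baselines are of the same kind, so a same-day baseline cannot be the reason for limiting caffeine in one test only.

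**Step 4. What the same-day baseline does and does not remove.** Suppose caffeine taken before arrival shifts FEV1 by a constant amount. The shift is present at baseline and afterwards and largely drops out of the fall. Two things do not drop out: caffeine taken after the baseline reading, and caffeine present at baseline that wears off later. The time available is long. Monitoring runs up to 10 hours after the last dose. A subject who takes diluent and all 12 concentrations once, at 10-minute intervals, spends 13 x 10 = 130 minutes on the ladder first. Subjects who stop early spend less, and asymptomatic subjects with a fall below 10% leave after 2 hours.

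**Step 5. Direction.** Assume, for the argument, that caffeine raises FEV1. Taken during monitoring, it would make the late fall look smaller. Present at baseline and then wearing off, it would make the late fall look larger. A blunted early fall would also lead to more allergen under the escalation rule, which may offset the blunting. The sign is therefore undetermined.

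**Step 6. HRV.** Visit 2 is under the limit and Visit 3 is not. A Visit 3 minus Visit 2 difference equals challenge effect plus any effect of the caffeine difference plus other day-to-day differences. A reference taken from Visit 3 before the challenge removes the between-day part, and the device is already in place (item 3, with the challenge at item 8).

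**The case against.** The strongest reply is that the documents connect caffeine with methacholine testing only. They never say that it alters an allergen-induced early or late fall, and they give no effect size. The same-day baseline removes a steady shift, and titration to a 20% fall may compensate for a blunted early response. The trial is a single-arm screening study, so no treatment comparison can be biased. No Visit 2 versus Visit 3 HRV contrast is specified, and Visit 2 subjects are asked only to limit caffeine, so that baseline is not caffeine-free either. Instructions to subjects may also sit in worksheets or consent pages that are not available here.

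Most of this stands, and it rules out several stronger readings that a reader might infer:

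- That true late responders are missed. Neither the size nor the direction of an effect is established.
- That the loss can be put as a percentage. One could take the cited cat-challenge study ("During the LPR, the mean drop in FEV1 was 17"%) and subtract an assumed caffeine effect to see how many subjects drop below 15%. The assumed effect would have no source in the documents, it would presuppose one direction, and the spread reported with that mean (1.9) is not labelled SD or SE.
- That excluding daily theophylline shows the plan regards caffeine as acting on the allergen readout. Exclusion 3c makes no link to caffeine.
- That challenge-day HRV is wholly confounded with caffeine. A same-day pre-challenge segment can be recorded.
- That intake is certainly unrecorded. One can say only that no listed Visit 3 procedure asks for it.

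The reply does not explain why caffeine is limited for one FEV1 readout with a same-day baseline and not for the other, and it does not deal with caffeine taken or wearing off during monitoring.

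**Conclusion.** The gap is confirmed by the text: caffeine is limited at Visits 2 and 4 and not at Visit 3, the only visit that yields the primary endpoint. The plan gives no reason for the difference. Any effect on the primary classification depends on caffeine affecting FEV1 during the stay and on subjects lying close to the 10%, 15% or 20% cut-offs. The documents allow neither to be quantified, so no estimate of bias is offered. For HRV, the problem arises only if Visit 3 is compared with the Visit 2 baseline, and the endpoint is exploratory. The point is minor: an inconsistency in measurement conditions that is worth removing because removal costs so little, not evidence that the study's result will be wrong.

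**What to change.** Reconcile the pre-test restrictions for Visits 2, 3 and 4 in sections 3.3, 4.2, 5.1, 5.4 and 9.4:

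1. Extend the existing caffeine instruction, in exclusion 1n and in the procedures, to the allergen challenge day until the end of monitoring.
2. Record caffeine intake at Visit 3, for example with the review of medical status, and update it during the stay.
3. State in section 6.3 that the reference for challenge-day HRV is the pre-challenge segment of the Visit 3 recording, with Visit 2 as supporting information.

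The cost is a few words in the protocol, one added item on the Visit 3 worksheet and one more caffeine-limited day for subjects. No visit, sample or device is added.
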